7.1.7.3. Exploratory Endpoints

The exploratory endpoints to measure glycemic control by CGM and SMBG will be evaluated, at each of the specified timepoints, compared to baseline. The analysis of CGM parameters and SMBG

parameters will be performed over the 2-week End of Treatment period after the final dose, compared to baseline. The exploratory endpoints analysis will be conducted in the PP and ITT Populations. The following exploratory endpoints include:

- Average 8h overnight duration (min) and percent time with hypoglycemia at thresholds of <70, <60, and <50 mg/dL (3.9, 3.3, and 2.8 mmol/L, respectively) by CGM
- Average 8h overnight hypoglycemia incidence (event rate) at each of the specified glucose thresholds by CGM
- Average daily and 8h overnight area over and under the glucose curve (AUC, AOC) for each of the specified glucose thresholds by CGM
- Average glucose level between midnight and 8:00 AM (or nearest pre-breakfast time point) by CGM
- Average weekly hypoglycemia incidence (event rate) at each of the specified glucose thresholds of <70, <60, and <50 mg/dL (3.9, 3.3, and 2.8 mmol/L, respectively) by SMBG

Additionally, Average weekly hyperglycemia incidence (event rate) at each of the specified glucose thresholds of >180, >250, and >300 mg/dL (10.0, 13.9 and 16.6 mmol/L, respectively) by SMBG

The derivations of above exploratory endpoints are presented in [section 4.1](#). The exploratory endpoints of actual and change from baseline values will be summarized by visit, cohort and RZ358 Total using descriptive statistics (n, Mean, SD, SE, Median, Minimum, Maximum and 95% CI for Mean). Along with these, First Quartile (Q1) and Third Quartile (Q3) will also be presented for duration (min) parameters. AOC and AUC of above glucose parameters will also be summarized by visit, cohort and RZ358 Total using descriptive statistics (n, Mean, SD, SE, CV (%), Geometric Mean, Geometric CV (%), Median, Minimum, Maximum and 95% CI for Geometric Mean). Within cohort comparative analysis will be performed using paired t test by comparing each post baseline visits with baseline visit, p-value from the test will be reported and analysis will be performed using ITT and PP Populations. Corresponding mean (SD) plots will also be produced for above endpoints to illustrate the descriptive statistics as appropriate.

Comparison of glycemic efficacy of RZ358 by CGM/SMBG endpoints

The within cohort comparison of post baseline visits to baseline visit in glycemic efficacy of CGM/ SMBG endpoints over the 2-week End of Treatment period after the final dose will be analyzed using paired t-test and p-value from the test will be reported.

The null and alternative hypothesis are,

$$H_0 : \mu_d = 0 \quad \text{and} \quad H_1 : \mu_d \neq 0$$

Where, μ_d is the mean difference in glycemic efficacy of CGM/SMBG parameters within cohort.

The normality of the CGM/SMBG endpoints will be performed using Shapiro-Wilk Test. If the p -value from the test result is normal, that is, p -value ≥ 0.05 , then paired t-test will be used; otherwise, a non-parametric Wilcoxon Sign Rank Test will be used.

Additional endpoints

Listings will be presented for the following additional endpoints.

- Intravenous or enteral nutritional (glucose/dextrose) supplementation
- Use of SoC or rescue medications for hypoglycemia (dextrose or other)

Pharmacodynamic Biomarker Analyses

Blood samples will be collected at scheduled timepoints, throughout the treatment periods of the study to evaluate the PD effects of the study drug. The PD of RZ358 compared to baseline will be assessed by:

- Average levels of glucose, insulin, c-peptide, glucagon, FFAs, and ketones (beta-hydroxybutarate), at each of the specified collection timepoints.

The actual and change from baseline values of the above parameters will be summarized using descriptive statistics (n, Mean, SD, SE, Median, Minimum, Maximum and 95% CI for Mean) at each of the specified collection timepoints by visit, cohort and RZ358 Total for the PP population.

- Incidence of safety fasting blood glucose values >200 , >250 , and >300 mg/dL (>11.1 , >13.9 , and >16.6 mmol/L, respectively).

Incidence of safety fasting blood glucose values >200 , >250 , and >300 mg/dL (>11.1 , >13.9 , and >16.6 mmol/L, respectively) will be summarized using frequency count and percentage at each of the specified collection timepoints by visit, cohort and RZ358 Total for the PP population.

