2.3. Determination of Sample Size

The sample size chosen for this study was selected without statistical considerations. It has been determined adequate to meet the study objectives. Patients who withdraw from the study may be replaced on a case-by-case basis after discussion and agreement with the Sponsor's Medical Monitor.

Up to approximately 24 to 32 patients are planned to be enrolled into this study if all cohorts are completed. Each of the (up to) 4 cohorts will comprise up to 6-8 patients to ensure there are a minimum of 3 patients \leq 10 years of age per cohort. Patients who discontinue the study before the Week 5 treatment and evaluation period may be replaced at the discretion of the Sponsor, if discontinuation was not due to a dose-limiting toxicity (DLT).

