If the year is after the year of first day on study medication, then January 1 will be assigned to the missing fields.

Missing month only

Treat day as missing and replace both month and day according to the above procedure.

Missing day only

- i. If the month and year are same as the year and month of first dose date of study medication, then the start date of study medication will be assigned to the missing day.
- ii. If either the year is before the year of the first dose date of study medication or if both years are the same, but the month is before the month of the first dose date of study medication, then the last day of the month will be assigned to the missing day.
- iii. If either the year is after the year of the first dose date of study medication or if both years are the same, but the month is after the month of the first dose date of study medication, then the first day of the month will be assigned to the missing day.

For AE Stop Date:

If the stop date is complete and the imputed start date as above is after the stop date, the start date will be imputed by the stop date.

If the stop date is incomplete, no imputation needed.

For CM End Date:

CM end date will not be imputed if CM ongoing is checked.

1. If the year is unknown, then do not impute the date but assign a missing value.
2. If the month is unknown, then assign “December.”
3. If the day is unknown, then assign the last day of the month.

If AE onset date is non-missing and is before the first dose date then the AE is considered to be prior treatment.

If AE onset date is non-missing and is occurred on the same date as the first dose with the event marked as start prior to first dose of study drug on the CRF then the AE is considered to be prior treatment.

If AE onset date is missing and is marked as start prior to the first dose of study drug on the CRF then the AE is considered to be prior treatment.

If CM start date is taken prior to the first dose of study drug regardless continuing to take the medication while on study treatment, then the CM is considered to be prior treatment.

Missing data imputation for Visit-Specific Assessments (e.g., safety labs, vital signs, hepatic ultrasound, 12-lead ECG):

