An unscheduled assessment (full visit or partial assessment) that is discrete and associated with a specific visit will be imputed as the scheduled assessment for the nearest visit where the applicable assessment is missing. Unscheduled data collected prior to the first dose will be assigned to the nearest missing screening visit or assessment (instead of nearest post-treatment visit). Unscheduled data collected after the final dose will be assigned to the nearest missing treatment or post-treatment visit or assessment. When an unscheduled assessment represents a value that is repeated (to a scheduled value, i.e., no missing data), then these will be adjudicated by medical review prior to database lock, to determine the value for the scheduled summary. If the unscheduled/repeat value affirms the legitimacy of the original value, the original value will be used and the unscheduled/repeat value will be additionally included in listings. When the value refutes the legitimacy of the original value

(suggesting spurious original value), the unscheduled/repeat value will be imputed to that scheduled visit, and the original value will be excluded from the dataset and listings.

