6. ANALYSIS POPULATION AND TREATMENT GROUPS

6.1. Analysis Population

ITT Population: All patients who are enrolled into the study.

Safety Population: All patients enrolled in the study who receive at least one dose of study drug.

Per protocol Population: All patients who receive at least 4 weeks of study drug (2 bi-weekly doses), with no major protocol violations. A patient in the Per protocol population may be excluded from one or more specific efficacy analyses (i.e. SMBG-related endpoints or CGM-related endpoints), if they have a major protocol deviation affecting only that endpoint (e.g. non-compliance with SMBG only, or non-compliance with CGM only).

PK Population: All patients who receive study drug and have a sufficient number and quality (biologically plausible) of results.

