Glycemic efficacy of RZ358 as evaluated by the average daily percent time within a glucose target range of 70-250 mg/dL (3.9-13.9 mmol/L) by CGM	Descriptive statistics, Paired T-test (analyzing post baseline visits with baseline visit)	PP Population and ITT Population	No imputation	Average daily percent time, cohort	8 Weeks /EOT
Average 8h overnight percent time in glucose target range of 70-250 mg/dL (3.9-13.9 mmol/L) by CGM	Descriptive statistics, Paired T-test (analyzing post baseline visits with baseline visit)	PP Population and ITT Population	No imputation	Average 8h overnight percent time, cohort	8 Weeks /EOT

Endpoint	Statistical Method / Test	Analysis Population	Missing Data Imputation Approach	Parameters/Variables in the analysis (Stat. test/Model)	Analysis Time point
Average weekly hyperglycemia incidence (event rate) at each of the specified glucose thresholds of >180, >250, and >300 mg/dL (10.0, 13.9 and 16.6 mmol/L, respectively) by SMBG	Descriptive statistics Paired T-test (analyzing post baseline visits with baseline visit)	PP Population and ITT Population	No imputation	Average weekly hyperglycemia incidence, cohort	8 Weeks /EOT
Incidence of fasting blood glucose values >200, >250, and >300 mg/dL (>11.1, >13.9, and >16.6 mmol/L, respectively)	Count and percentage	PP Population	No imputation	eCRF	8 Weeks /EOT
PD Markers of RZ358 activity including fasting levels of glucose, insulin, c-peptide, glucagon, FFAs, and ketones (beta-hydroxybutarate).	Descriptive statistics	PP Population	No imputation	eCRF	8 Weeks /EOT

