7.1.8. Safety Analysis

The analysis of primary safety endpoints will include assessments of AEs, vital signs, 12-lead ECGs, infusion-site observations, physical examination, hepatic ultrasound results, and clinical laboratory evaluations including glucose values. All safety analyses will be performed using the Safety Population.

Adverse Events:

Adverse Events will be coded using (MedDRA version 25.0 Mar 2022) AE coding system for the purpose of summary tables. Treatment-emergent adverse events (TEAE) will be summarized by cohorts and RZ358 Total and AEs that are non-TEAE will be identified.

For each cohort, AEs will be summarized with frequency count and percentage by MedDRA SOC and PT, with all patients treated in that cohort as the denominator, unless otherwise specified. In addition, AEs will also be summarized by severity and relationship to study drug.

All AEs and TEAEs during the study will be summarized for the respective cohorts. A patient experiencing the same AEs and TEAEs multiple times will be counted only once for that PT. Similarly, if a patient experiences multiple AEs and TEAEs (preferred terms) within the same SOC then that patient will be counted only once for that SOC. When summarizing by severity, the event with highest severity will be counted. All AEs will be listed in chronological order of the events occurred.

For purposes of this study, TEAEs for summary tabulation will be further defined as those events which occur within a period of time through the +42 days follow-up visit after the final dose of study drug. Adverse events with onset after ICF but before first dose of study drug or after last dose of study drug +42 days will be identified separately from TEAEs.

Summary tables of the following AEs will be provided:

An overview of TEAE summary will be presented by cohorts, and it will include:

- Number of Subjects with any TEAEs
- Number of subjects with any TEAEs related to study drug
- Number of subjects with any TEAEs leading to treatment/study discontinuation
- Number of subjects with TEAEs by maximum severity grade
- Number of Subjects with any serious TEAEs
- Number of Subjects with any serious TEAEs related to study drug
- Number of Subjects with any serious TEAEs leading to treatment/study discontinuation
- Number of Subjects with any serious TEAEs leading to death

➤ Number of subjects with any non-TEAEs

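### Fasting glucose above 200, 250 and 300 mg/dL is counted in the per-protocol population only, and no visible table counts it in all dosed patients

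*SAP*

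**What the plan says.** SAP 7.1.7.3, under the pharmacodynamic biomarker analyses, introduces the measure as "Incidence of safety fasting blood glucose values" above 200, 250 and 300 mg/dL and plans a "frequency count and percentage at each of the specified collection timepoints by visit, cohort and RZ358 Total for the PP population". The matching row in SAP 7.1.7.4, "Incidence of fasting blood glucose values >200, >250, and >300 mg/dL", also names PP alone, rules out imputation, and gives 8 Weeks/EOT as the only analysis timepoint. In the same table the CGM, SMBG and fasting-challenge rows carry both PP and ITT.

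SAP 6.1 defines PP as "All patients who receive at least 4 weeks of study drug (2 bi-weekly doses), with no major protocol violations". It adds that a patient whose major deviation affects only CGM or only SMBG may be dropped from those analyses alone. The Safety Population is everyone with at least one dose.

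SAP 7.1.8 lists among the safety assessments "clinical laboratory evaluations including glucose values. All safety analyses will be performed using the Safety Population". The protocol synopsis likewise bases safety reporting on all patients who received a dose.

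On unscheduled values, SAP Section 3 keeps them out of tables unless its assignment rules are met. Those rules are titled "Missing data imputation for Visit-Specific Assessments (e.g., safety labs, vital signs, hepatic ultrasound, 12-lead ECG" and include: "Unscheduled data collected after the final dose will be assigned to the nearest missing treatment or post-treatment visit or assessment".

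**The concern.** A count described as safety would normally include every dosed patient. Here a patient who received one infusion, or who had a major violation of a general kind, is left out even if a fasting sample was taken and was high. Early stopping may also be related to tolerability: Protocol 4.5.1 lists adverse events among the reasons for withdrawal. Patients who stop early can be replaced ("Patients who discontinue the study before the Week 5 treatment and evaluation period may be replaced at the discretion of the Sponsor", provided the cause was not a dose-limiting toxicity), so the PP count may rest partly on replacements.

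At stake is the only visible table that says how many patients crossed these three fasting cut-offs. With 6 to 8 patients per cohort, one patient moves the percentage a good deal. Two reporting details add uncertainty: the two SAP sections disagree on timepoints, and it is unclear whether an unscheduled fasting value can reach the table.

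**Working it through.** There is no figure in the plan to reproduce: the sample size was chosen without statistical considerations, and no event or exclusion rates are given. The check is a comparison of texts and a simple illustration.

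**1. Which population applies**

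- SAP 7.1.7.3 text: PP.
- SAP 7.1.7.4 row: PP.
- The general sentence in 7.1.7.3 naming both PP and ITT for exploratory endpoints introduces a list of CGM and SMBG endpoints only. The later, specific text governs fasting glucose.
- SAP 7.1.8: Safety Population. The visible outputs are n, mean, SD, median, minimum and maximum by visit, Low/Normal/High shifts, and listings. None is a count above 200, 250 or 300 mg/dL.
- SMBG hyperglycemia rates: ITT and PP, at cut-offs of 180, 250 and 300 mg/dL. They are not fasting laboratory values and have no 200 mg/dL cut.

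The PP restriction is therefore stated twice, and no visible table gives the counts in all dosed patients.

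**2. What one patient does to the percentage**

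SAP Section 3 sets the percentage as 100 × n/N, with N the number in the stated population. Let N be the patients first dosed in a cohort, x those outside PP, and r replacements who enter PP unaffected. Then Safety % = 100 × affected/(N + r) and PP % = 100 × affected and retained/(N − x + r). Cohort sizes of 6 and 8 are the planned limits. The numbers affected and excluded are assumptions. The high value is assumed to reach the by-visit table.

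| Assumed case | N = 8: Safety vs PP | N = 6: Safety vs PP |
|---|---|---|
| One affected, outside PP, not replaced | 1/8 = 12.5% vs 0/7 = 0% | 1/6 = 16.7% vs 0/5 = 0% |
| Same patient, replaced | 1/9 = 11.1% vs 0/8 = 0% | 1/7 = 14.3% vs 0/6 = 0% |
| Two affected, one of them outside PP | 2/8 = 25.0% vs 1/7 = 14.3% | 2/6 = 33.3% vs 1/5 = 20.0% |
| One affected and kept, one unaffected outside PP | 1/8 = 12.5% vs 1/7 = 14.3% | 1/6 = 16.7% vs 1/5 = 20.0% |
| Nobody outside PP | equal | equal |

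For RZ358 Total, one affected patient outside PP and not replaced gives 1/24 = 4.2% or 1/32 = 3.1% in Safety against 0% in PP. The last two cohort cases show that PP can also read higher than Safety, or the same.

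**3. Timepoints**

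The 7.1.7.3 text plans every collection timepoint; the 7.1.7.4 row names 8 Weeks/EOT alone. A patient who stops after one dose may have no value at that timepoint. Under the row as written, such a patient would add nothing to the numerator even in a Safety Population table: 0/8 rather than 1/8. Changing the population without settling the timepoint would therefore not be enough.

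**4. Unscheduled values**

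Section 3 names safety laboratory tests and assigns unscheduled results to the nearest missing visit, calling this imputation. The 7.1.7.4 row excludes imputation. The text does not say which governs this table.

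**The case against.** The strongest reply is that PP is what the protocol directs. Protocol 2.3 lists the measure as exploratory, Protocol 6.3.3 as pharmacodynamic, and Protocol 7.7 puts the primary PD analysis in PP. The SAP places the measure under PD, and the rule in 7.1.8 opens a different section. This stands: a reader might infer that the SAP departs from the protocol, and it does not. What remains is the SAP's own safety label, and the fact that a rule for the primary PD analysis does not prevent a second table.

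A reader might also infer that high fasting glucose disappears from safety reporting. It does not. Section 7.1.8 includes glucose among the laboratory evaluations. In cohorts this small, a by-visit maximum in the Safety Population would show whether any summarised value passed a cut-off, and the listings show individual values. SMBG rates are also reported for ITT. What is missing is the number of patients above each cut-off.

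A third tempting reading is that replacement hides an excluded patient. The disposition table in SAP 7.1.1 reports Safety and PP numbers and reasons for discontinuation by cohort, and table headers show N, so any gap is visible. The second sentence of the PP definition also narrows the loss, since deviations confined to CGM or SMBG need not remove a patient from this table.

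Finally, parts of 7.1.8 are redacted and the mock tables are not supplied, so a Safety Population threshold table may exist. The point is limited to the visible text.

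**Conclusion.** The point holds as a minor one. A hyperglycemia count that the SAP labels as safety is planned only in PP, and no visible table gives it for all dosed patients. Those left out are patients with fewer than two bi-weekly doses, or with a major violation not confined to CGM or SMBG.

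If one such patient had a high fasting value that reached the table, the cohort figure would be 12.5% (N = 8) or 16.7% (N = 6) in Safety and 0% in PP. These figures rest on assumed numbers affected and excluded. The documents do not support a claim about the direction or likely size of any actual difference, and there is none if every dosed patient is in PP.

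**What to change.** In SAP 7.1.7.3 and 7.1.7.4:

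1. Add the same threshold table (count and percentage above 200, 250 and 300 mg/dL, by visit, cohort and RZ358 Total) in the Safety Population, and keep the PP table as the PD view.
2. Reconcile the timepoints in favour of by-visit reporting, by amending the 8 Weeks/EOT entry in the 7.1.7.4 row, so that patients who stop early are counted at the visits where they have values.
3. State that the Section 3 rule for unscheduled safety laboratory values applies identically to both tables, and correct the imputation entry in the 7.1.7.4 row to match. Applying the rule to one table only would make the two differ in data handling as well as in population.

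The cost is one extra descriptive table from existing data, using the same program with a different population flag, and small text corrections in two sections.

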7.1.7.4. Summary of Efficacy Endpoint Analysis Strategy

Endpoint	Statistical Method / Test	Analysis Population	Missing Data Imputation Approach	Parameters/Variables in the analysis (Stat. test/Model)	Analysis Time point
Primary Endpoint					
Glycemic efficacy of RZ358 as evaluated by the average daily percent time within a glucose target range of 70-180 mg/dL (3.9-10 mmol/L) by CGM	Descriptive statistics, Paired T-test (analyzing post baseline visits with baseline visit)	PP Population and ITT Population	No imputation	Average daily percent time, cohort	8 Weeks /EOT
Secondary Endpoint					
Average weekly incidence of hypoglycemia (< 70 mg/dL) by self-monitored blood glucose (SMBG)	Descriptive statistics, Paired T-test (analyzing post baseline visits with baseline visit)	PP Population and ITT Population	No imputation	Average weekly incidence, cohort	8 Weeks /EOT

Endpoint	Statistical Method / Test	Analysis Population	Missing Data Imputation Approach	Parameters/Variables in the analysis (Stat. test/Model)	Analysis Time point
Average daily duration (min) and percent time with hypoglycemia at thresholds of <70, <60, and <50 mg/dL (3.9, 3.3, and 2.8 mmol/L, respectively) by CGM	Descriptive statistics, Paired T-test (analyzing post baseline visits with baseline visit)	PP Population and ITT Population	No imputation	Average daily duration, Average daily percent time, cohort	8 Weeks /EOT
Average daily hypoglycemia incidence (event rate) at each of the specified glucose thresholds by CGM	Descriptive statistics, Paired T-test (analyzing post baseline visits with baseline visit)	PP Population and ITT Population	No imputation	Average daily hypoglycemia incidence, cohort	8 Weeks /EOT
Average 8h overnight percent time in glucose target range of 70-180 mg/dL (3.9-10 mmol/L) by CGM	Descriptive statistics, Paired T-test (analyzing post baseline visits with baseline visit)	PP Population and ITT Population	No imputation	Average 8h overnight percent time, cohort	8 Weeks /EOT

Endpoint	Statistical Method / Test	Analysis Population	Missing Data Imputation Approach	Parameters/Variables in the analysis (Stat. test/Model)	Analysis Time point
Occurrence of hypoglycemia during a 12h fasting challenge. (Percentage of patients able to complete a fast)	Count and percentage, Comparison of proportions using McNemar Test.	PP Population and ITT Population	No imputation	eCRF	Week 7
Occurrence of hypoglycemia during a 12h fasting challenge. (Time to termination of fast, Glucose nadir during fast, Ketone levels at the conclusion of fast)	Descriptive statistics, Paired T-test (analyzing post baseline visits with baseline visit)	PP Population and ITT Population	No imputation	eCRF	Week 7
Additional Exploratory Endpoints					
Average 8h overnight duration (min) and percent time with hypoglycemia at thresholds of <70, <60, and <50 mg/dL (3.9, 3.3, and 2.8 mmol/L, respectively) by CGM	Descriptive statistics, Paired T-test (analyzing post baseline visits with baseline visit)	PP Population and ITT Population	No imputation	Average 8h overnight duration, Average 8h overnight percent time, cohort	8 Weeks /EOT

Endpoint	Statistical Method / Test	Analysis Population	Missing Data Imputation Approach	Parameters/Variables in the analysis (Stat. test/Model)	Analysis Time point
Average 8h overnight hypoglycemia incidence (event rate) at each of the specified glucose thresholds by CGM	Descriptive statistics, Paired T-test (analyzing post baseline visits with baseline visit)	PP Population and ITT Population	No imputation	Average 8h overnight hypoglycemia incidence, cohort	8 Weeks /EOT
Average daily and 8h overnight area over and under the glucose curve (AUC, AOC) for each of the specified glucose thresholds by CGM	Descriptive statistics, Paired T-test (analyzing post baseline visits with baseline visit)	PP Population and ITT Population	No imputation	Average daily and 8h overnight AUC & AOC, cohort	8 Weeks /EOT
Average glucose level between midnight and 8:00 AM (or nearest pre-breakfast time point) by CGM	Descriptive statistics, Paired T-test (analyzing post baseline visits with baseline visit)	PP Population and ITT Population	No imputation	Average glucose level between midnight and 8:00 AM, Cohort	8 Weeks /EOT

Endpoint	Statistical Method / Test	Analysis Population	Missing Data Imputation Approach	Parameters/Variables in the analysis (Stat. test/Model)	Analysis Time point
Average weekly hypoglycemia incidence (event rate) at each of the specified glucose thresholds by SMBG	Descriptive statistics Paired T-test (analyzing post baseline visits with baseline visit)	PP Population and ITT Population	No imputation	Average weekly hypoglycemia incidence, cohort	8 Weeks /EOT
Glycemic efficacy of RZ358 as evaluated by the average daily percent time within a glucose target range of 70-250 mg/dL (3.9-13.9 mmol/L) by CGM	Descriptive statistics, Paired T-test (analyzing post baseline visits with baseline visit)	PP Population and ITT Population	No imputation	Average daily percent time, cohort	8 Weeks /EOT
Average 8h overnight percent time in glucose target range of 70-250 mg/dL (3.9-13.9 mmol/L) by CGM	Descriptive statistics, Paired T-test (analyzing post baseline visits with baseline visit)	PP Population and ITT Population	No imputation	Average 8h overnight percent time, cohort	8 Weeks /EOT

Endpoint	Statistical Method / Test	Analysis Population	Missing Data Imputation Approach	Parameters/Variables in the analysis (Stat. test/Model)	Analysis Time point
Average weekly hyperglycemia incidence (event rate) at each of the specified glucose thresholds of >180, >250, and >300 mg/dL (10.0, 13.9 and 16.6 mmol/L, respectively) by SMBG	Descriptive statistics Paired T-test (analyzing post baseline visits with baseline visit)	PP Population and ITT Population	No imputation	Average weekly hyperglycemia incidence, cohort	8 Weeks /EOT
Incidence of fasting blood glucose values >200, >250, and >300 mg/dL (>11.1, >13.9, and >16.6 mmol/L, respectively)	Count and percentage	PP Population	No imputation	eCRF	8 Weeks /EOT
PD Markers of RZ358 activity including fasting levels of glucose, insulin, c-peptide, glucagon, FFAs, and ketones (beta-hydroxybutarate).	Descriptive statistics	PP Population	No imputation	eCRF	8 Weeks /EOT

